6.12.4. Vital Signs

Descriptive summaries will be provided for vital signs (respiration, pulse, temperature, systolic blood pressure, diastolic blood pressure) measured at each visit and time point, as well as their changes from baseline.

To evaluate the clinical significance of vital sign indicators, a cross-tabulation will be used to summarize the changes in subjects' clinical assessment categories from baseline to the worst post-baseline clinical assessment category (abnormal with clinical significance > abnormal without clinical significance > normal > not examined).

List the vital signs of the subjects in detail.

6.12.5. Physical Examination

For the clinical significance evaluation of each body part or system in physical examinations, a cross-tabulation will be used to summarize the changes in subjects' clinical assessment categories from baseline to the worst post-baseline clinical assessment category (clinically significant abnormality > abnormality without clinical significance > normal > not examined).

List the physical examination results of the subjects.

6.12.6. 12-lead ECG

Descriptive statistics will be performed on the ECG parameters (heart rate, PR interval, QRS duration, uncorrected QT interval, and QTcF corrected by Fridericia's formula) measured at each visit and time point, as well as their changes from baseline.

For the assessment of clinical significance of electrocardiograms, a cross-tabulation will be used to summarize the changes in subjects' clinical assessment categories from baseline to the worst post-baseline clinical assessment category (abnormal with clinical significance > abnormal without clinical significance > normal > not performed).

For continuous variables summarized by visit and time point, the average of two replicate measurements will be used as the baseline value and post-baseline analysis value. When summarized by clinical significance assessment, the average of two repeated assessments will be used as the baseline value, and the worst clinical assessment post-baseline will serve as the post-baseline analysis value.

List the ECG examination results of subjects in detail.

6.13. Other Evaluations

Based on the FAS, detailed listings will be provided for infectious disease screening, B-ultrasound, tumor marker testing, serum follicle-stimulating hormone (FSH) testing, blood/urine pregnancy testing, modified Hoehn-Yahr scale assessment, and orthostatic hypotension testing.

6.14. Sub-group Analysis

If the data permit, subgroup analyses of drug exposure will be conducted by age group, with subgroups categorized as:

- Age groups (<18 years, 18-65 years, 66-75 years, >75 years)

If the data permit, subgroup analyses for the primary endpoint will be conducted using the same statistical methods as the primary analysis. Subgroup categories include:

- Whether the subject will be stably receiving levodopa as the basic anti-PD medication (Yes, No)
- Medications for Anti-Parkinson's Disease:
 - No prior anti-PD therapy
 - Previous anti-PD therapy but no anti-PD therapy within 4 weeks prior to enrollment
 - Patients must have received stable anti-PD drug therapy for at least 4 weeks prior to enrollment and agree to maintain the original treatment regimen unchanged during the trial.
- Age group at initial diagnosis (≤ 50 years, > 50 years)

If applicable, subgroup analyses will also be performed for MDS-UPDRS score-related secondary endpoints.

7. Interim Analysis

Not applicable

8. Changes to the Planned Analysis of the Protocol

None

9. References

None

10. Statistical Chart Templates and Dataset Programming Specifications

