3.4.3. Assessment of Skeletal Muscle Mass and Function

The exploratory skeletal muscle mass and function assessment indicators in this trial include ASMI, muscle strength (handgrip strength), and the 6-meter walk test. The specific testing indicators should be determined based on the actual operations of each center.

4. Sample Size

The sample size of this study is not determined based on the formal statistical assumptions and it is expected to include approximately 150 subjects with early-stage PD, who will be randomized in a 1:1 ratio into two cohorts (Cohort 1: 200 mg dose group; Cohort 2: 400 mg dose group). Within each cohort, the subjects will be randomized into the TJ0113 capsules group and the placebo group in a ratio of 2:1, with approximately 50 subjects receiving TJ0113 capsules and approximately 25 subjects receiving the placebo. In this study, there will be approximately 50 subjects in each of the TJ0113 capsules 200 mg group, TJ0113 capsules 400 mg group and the placebo group.

5. Analysis Sets

Full analysis set (FAS): including all randomized subjects who have received at least one dose of investigational product.

Per-protocol set (PPS): including subjects in the FAS who have not experienced major protocol deviations that affect the primary efficacy endpoint.

Safety Set (SS): Includes all subjects who received at least one dose of the investigational product and underwent at least one post-dose safety assessment.

Demographics and baseline characteristics will be analyzed based on FAS, the efficacy analyses will be performed based on both FAS and PPS, and the safety analyses will be performed based on SS.

6. Statistical Analysis Methods

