A Mixed Model for Repeated Measures (MMRM) will be used to calculate nominal P values for between-group comparisons of primary and secondary endpoints; where applicable, analysis of covariance (ANCOVA) will be employed to calculate nominal P values for between-group comparisons of primary endpoints. For exploratory endpoints with normally distributed variables, analysis of variance (ANOVA) will be used to calculate nominal P-values for between-group comparisons; otherwise, the Wilcoxon rank-sum test will be employed for between-group comparisons to calculate nominal P-values.

Confidence Interval (CI)

Unless otherwise specified, the CI refers to a two-sided 95% CI, with one more decimal place than the derived data or parameters.

P-value

This study does not conduct formal hypothesis testing, and the summarized P-values will be nominal P-values. P-values should be retained to 4 decimal places. If the P-value is less than 0.0001, it should be presented as "<.0001"; if the P-value will be greater than 0.9999, it should be presented as ">.9999".

Treatment Group

Unless otherwise specified, it will be summarized by the TJ0113 capsules 200 mg group, TJ0113 capsules 400 mg group, and the placebo group.

Study Day 1

Study Day 1 is defined as the day of the first dose of the investigational product. All safety and efficacy assessments will be calculated based on Study Day 1.

- If the visit date \geq the first dose date, then: Study day = Visit date - First dose date + 1
- If the visit date $<$ the first dose date, then: Study day = Visit date - First dose date.

There is no definition of Study Day 0 in this study.

Repeated Measurements or Assessments

If more than one measurement or assessment of a certain parameter is conducted at the same time point during the same visit according to the study protocol, it will be defined as a repeated measurement or assessment. The mean value of repeated measurements or evaluations will be used as the analytical value. In this study, all 12-lead electrocardiogram (ECG) parameters will be measured twice, and clinical evaluations will be performed with duplicate assessments.

Baseline Value

Unless otherwise specified, baseline is defined as the last valid measurement or assessment result prior to the first dose (including scheduled or unscheduled visits). If an unscheduled visit date coincides with the scheduled visit date and the exact time is unknown, the results from the scheduled visit should be used as the baseline.

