6.10.1.1. Primary Analysis

The analysis will be performed using a mixed models for repeated measures (MMRM) with the changes from baseline in the MDS-UPDRS Part III scores after 12 weeks of treatment as the dependent variable, whether subjects have been receiving levodopa, the background medication for PD (yes vs. no) at a stable dose at baseline and the baseline MDS-UPDRS Part III score as the covariates, and the treatment group, visit, and the treatment group-by-visit interaction as the fixed effects. The covariance matrix prioritizes an unstructured (UN) covariance matrix. If the results do not converge, the following covariance structures will be tested sequentially: heterogeneous Toeplitz (TOEP), first-order autoregressive (AR1), and compound symmetry (CS). The first covariance structure that achieves convergence will be used. Based on the model, calculate the least squares mean of the change from baseline in MDS-UPDRS Part III score at 12 weeks of treatment, along with its 95% CI, the between-group difference in least squares means with its two-sided 95% CI, and the nominal P-value.

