Step 3: The imputed complete data from Step 2 will be used for statistical analysis. First, the endpoint value will be calculated: the change from baseline in the Movement Disorder Society-Unified Parkinson's Disease Rating Scale (MDS-UPDRS) Part III (Motor Examination) score after 12 weeks of treatment (evaluation time point: ≥ 12 hours since the last dose of anti-PD medication). Then, recalculate the statistical measures for this endpoint (such as least squares mean differences and standard errors) to

obtain the statistical measures for 100 iterations. The reference program for the SAS PROC MIXED procedure is as follows:

```
PROC MIXED DATA=ANA_IMPUT4;  
  BY _imputation_;  
  CLASS pd trtpn avisitn usubjid;  
  MODEL chg = pd base trtpn avisitn avisitn*trtpn /ddfm=kenwardroger htype=3;  
  REPEATED avisitn/subject=usubjid type=&type:;  
  LSMEANS avisitn*trtpn/cl diff;  
  ODS OUTPUT lsmeans=mixedlsmeans1 diffs=diff1;  
run;
```

Step 4: Combine the 100 statistics using Rubin's method to obtain the pooled statistic, which serves as the final statistic for analysis. The reference program for the SAS PROC MIANALYZE procedure is as follows:

```
PROC MIANALYZE DATA=formianalyze;  
  MODELEFFECTS estimate;  
  STDERR stderr;  
RUN;
```

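### The subgroup plan reports a nominal P-value in each subgroup but no estimate of how the treatment effect differs between subgroups

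*SAP*

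**What the plan says.** Protocol 11.4.6 defers subgroup detail to the SAP. SAP 6.14 makes the analyses conditional on the data permitting and states that "subgroup analyses for the primary endpoint will be conducted using the same statistical methods as the primary analysis". It lists three factors for the primary endpoint: levodopa use (two levels), anti-PD medication history (three levels) and age at initial diagnosis (two levels). It may extend them to the MDS-UPDRS secondary endpoints.

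The primary method is in SAP 6.10.1.1. It is an MMRM with levodopa use and baseline score as covariates and "the treatment group, visit, and the treatment group-by-visit interaction as the fixed effects". Its output is a least squares mean per group, "the between-group difference in least squares means with its two-sided 95% CI, and the nominal P-value". The reference code in SAP Appendix 11.1 carries the same terms: "MODEL chg = pd base trtpn avisitn avisitn*trtpn".

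On the status of the P-values, SAP 6.1 says: "This study does not conduct formal hypothesis testing, and the summarized P-values will be nominal P-values".

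None of Protocol 11.4.6, SAP 6.1, SAP 6.10 or SAP 6.14 names a treatment-by-subgroup term, an estimate of heterogeneity, or a rule for reading results across subgroups.

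**The concern.** A subgroup analysis asks whether the treatment effect differs between kinds of patient. The primary model has no treatment-by-subgroup term. Applied unchanged, it can give subgroup-specific effects only by being refitted within each subgroup. The SAP does not use those words, so separate fits are an inference, but there is no other natural reading.

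The result would be seven subgroups by two doses, that is 14 treatment differences for the primary endpoint, each with a nominal P-value, and no line comparing one subgroup with another. A reader who wants that comparison has the paired P-values to hand. One below 0.05 and one above it can easily arise when the effect is the same in both, because each subgroup has only part of the sample and the two parts may be unequal. At stake is a false impression of effect modification, or a missed one, in a trial that stratifies on one of these factors.

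**Working it through.** **Inputs from the documents.** SAP section 4 says "there will be approximately 50 subjects in each of the TJ0113 capsules 200 mg group, TJ0113 capsules 400 mg group and the placebo group". The allocation agrees: 150 × 1/2 × 2/3 = 50 per dose, and 2 × 25 = 50 on placebo. So each dose comparison is 50 against 50. SAP 6.1 gives the interval convention: "Unless otherwise specified, the CI refers to a two-sided 95% CI".

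**Assumptions.** No effect size, SD, power or subgroup share is given; SAP section 4 states that "The sample size of this study is not determined based on the formal statistical assumptions". There is therefore no plan figure to reproduce. I take:
- a uniform standardised effect d, in units of the SD of the Week 12 change;
- a share f of each arm in the larger subgroup, from 0.5 to 0.9;
- a two-sided 0.05 cut-off, to match the 95% CI;
- a normal approximation with known SD. This is optimistic for very small subgroups, such as 5 per arm at a 90/10 split.

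**Formulas.** With n patients per arm in a subgroup (n = 50f or 50(1−f)):
- SE = √(2/n)
- power p = Φ(d/SE − 1.96) + Φ(−d/SE − 1.96)
- the two subgroups contain different patients, so P(exactly one has P<0.05) = p₁(1−p₂) + p₂(1−p₁).

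**Reference effects.** In the full comparison SE = √(2/50) = 0.20. Power of 50% needs d = 1.96 × 0.20 = 0.39. Power of 80% needs d = (1.96 + 0.84) × 0.20 = 0.56.

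**Worked cases at d = 0.56.**
- 50/50: n = 25, SE = 0.283, d/SE = 1.98, p = 0.51 in both. Exactly one: 2 × 0.51 × 0.49 = 0.50.
- 70/30: n = 35 and 15, p = 0.649 and 0.335. Exactly one: 0.649 × 0.665 + 0.335 × 0.351 = 0.55.
- 90/10: n = 45 and 5, p = 0.757 and 0.144. Exactly one: 0.757 × 0.856 + 0.144 × 0.243 = 0.68.

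**Chance that exactly one of two subgroups has nominal P<0.05 when the effect is the same in both:**

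| Effect (SD) | Full-sample power | 50/50 | 70/30 | 90/10 |
|---|---|---|---|---|
| 0 | n/a | 9.5% | 9.5% | 9.5% |
| 0.20 | 17% | 19% | 20% | 20% |
| 0.39 | 50% | 41% | 42% | 47% |
| 0.56 | 80% | 50% | 55% | 68% |
| 0.80 | 98% | 31% | 42% | 74% |

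For equal subgroups the figure is 2p(1−p), which cannot exceed 50%, and 0.56 SD lies almost at that peak. The whole range should be read, not that row alone.

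**What a direct comparison gives.** A simulation of single-visit normal data (2,000 trials per setting; d of 0, 0.4 and 0.56; levodopa share 50% or 70%) tested the treatment-by-levodopa interaction under a uniform effect. It was nominally significant in 4.2% to 5.8% of trials, about 5% as it should be, at every effect size tried.

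**Its precision.** SE of the between-subgroup difference = √(2/(50f) + 2/(50(1−f))):
- 50/50: 0.40, half-width 1.96 × 0.40 = 0.78 SD
- 70/30: 0.436, half-width 0.86 SD
- 90/10: 0.667, half-width 1.31 SD

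These SEs are 2.0, 2.2 and 3.3 times the full-sample SE of 0.20.

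**The case against.** **The P-values are nominal and nothing is tested.** This is true, and the SAP sets no threshold and no rule for declaring a subgroup effect. A reader might infer from the table that a uniform effect will often be misread as working in one subgroup and not in the other. The documents do not support that: the calculation gives the chance of discordant P-values, not of a wrong conclusion, and that chance is about 10% at no effect and 19-20% at 0.20 SD. What remains is that labelling P-values nominal neither supplies the missing estimate nor tells the reader not to compare them.

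**The difference can be recovered by hand.** Separate fits use disjoint patients, so the between-subgroup difference and its SE, √(SE₁² + SE₂²), follow from the planned estimates and intervals. This stands and limits the harm, but the SAP does not plan the step. The table templates are in a separate file that was not available.

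**Separate fits are technically workable.** The levodopa covariate is constant within each levodopa subgroup and simply drops out. Non-convergence of the unstructured covariance has a listed fallback sequence, and small subgroups may be skipped under the data-permitting condition. These points stand. A residual weakness is that two separate fits may end with different covariance structures.

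**The stakes are not in the documents.** A reader might infer that levodopa-treated against untreated is the key question for choosing the next trial's population. No objective or endpoint says so. Levodopa use is the stratification factor, a covariate and one of three subgroup factors, and no more can be claimed.

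**The direct estimate will be imprecise.** This is correct, and it is a reason to show an interval rather than a pass/fail test.

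**Conclusion.** The point holds as a cheap improvement to an exploratory analysis; it does not threaten the primary result. The SAP plans subgroup-specific effects with nominal P-values, by separate fits on the natural but inferred reading, and does not plan the between-subgroup difference. Under a uniform effect with 50 per arm and splits from 50/50 to 90/10, exactly one of two subgroups would have nominal P<0.05 with probability of about 10% at no effect, 19-20% at 0.20 SD, 41-47% at 0.39 SD and 50-68% at 0.56 SD. Paired P-values are thus an unreliable guide to effect modification, most clearly when the drug has a moderate effect. The effects, the splits and the 0.05 cut-off are assumptions.

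**What to change.** In SAP 6.14, replace the reference to the primary method with one FAS model per factor. It would hold the primary MMRM terms plus subgroup, subgroup-by-visit, treatment-by-subgroup and treatment-by-subgroup-by-visit. For the levodopa factor the main effect is already in the model and should not be added again.

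For each dose against placebo, report:
- the Week 12 treatment difference in each subgroup, with its 95% CI;
- the between-subgroup difference, with its 95% CI.

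Omit within-subgroup P-values. The subgroup intervals can still be read as excluding zero or not, so the text should also state that heterogeneity is judged only on the between-subgroup estimate, and that an interval including zero does not show homogeneity.

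The cost is SAP wording and modest programming, with no new data. There are two downsides. The joint model assumes a common covariance across subgroups. The between-subgroup estimate will also be imprecise, with a 95% CI half-width of about 0.78 SD at a 50/50 split, 0.86 at 70/30 and 1.31 at 90/10.

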10.1. Statistical Chart Template

Refer to the separate Statistical Analysis Tables, Figures, and Listings Template file.

10.2. Dataset Programming Specifications

Refer to the separate SDTM/ADAM Spec files.

11. Appendices

11.1. Appendix A Multiple Imputation (MI) Method

MI will adhere to the following steps:

Step 1: For non-monotone missing data, assuming the missing mechanism is missing at random (MAR), the MCMC method will be used with 100 iterations for imputation. The corresponding SAS option will be MCMC IMPUTE = MONOTONE. The number of imputed seeds will be set to 12345. The upper and lower bounds of the MDS-UPDRS Part III (Motor Examination) score will be [0, 132], with imputed scores rounded to the nearest integer. If applicable, covariates include whether stable levodopa-based anti-PD medication was received at screening (yes vs. no), baseline values (base), and scores at post-baseline visits (weeks 1, 4, 8, and 12 of treatment). The order in which these variables enter the procedure step follows the sequence listed above. The imputed data constitutes monotone missing data, and these 100 datasets will be utilized in Step 2. The reference program for the SAS PROC MI procedure is as follows:

```
PROC MI DATA=adeff NIMPUTE=100 OUT=mi_monotone SEED=12345
```

```
ROUND=.. 1 1 1 1
```

```
MIN =.. 0 0 0 0
```

```
MAX =.. 132 132 132 132;
```

```
MCMC IMPUTE=MONOTONE;
```

```
VAR pd base week1 week4 week8 week12;
```

```
RUN;
```

Step 2: For the monotone missing data imputed in Step 1, assuming the missing mechanism is MAR, use the MONOTONE REG method for imputation. The corresponding SAS PROC MI option is MONOTONE REG. The missing values at post-baseline visits will be imputed using the results from the immediately preceding visit. The seed number for imputation will be set to 23456. The reference program for the SAS PROC MI procedure is as follows:

```
PROC MI DATA=mi_monotone NIMPUTE=1 OUT=mi_complete SEED=23456
```

```
ROUND=.. 1 1 1 1
```

```
MIN =.. 0 0 0 0
```

```
MAX =.. 132 132 132 132;
```

```
MINMAXITER=1000;
```

```
BY _imputation_;
```

```
CLASS pd;
```

```
VAR pd base week1 week4 week8 week12;
```

```
MONOTONE REG(pd base week1 week4 week8 week12);
```

```
RUN;
```

Step 3: The imputed complete data from Step 2 will be used for statistical analysis. First, the endpoint value will be calculated: the change from baseline in the Movement Disorder Society-Unified Parkinson's Disease Rating Scale (MDS-UPDRS) Part III (Motor Examination) score after 12 weeks of treatment (evaluation time point: ≥ 12 hours since the last dose of anti-PD medication). Then, recalculate the statistical measures for this endpoint (such as least squares mean differences and standard errors) to

obtain the statistical measures for 100 iterations. The reference program for the SAS PROC MIXED procedure is as follows:

```
PROC MIXED DATA=ANA_IMPUT4;  
  BY _imputation_;  
  CLASS pd trtpn avisitn usubjid;  
  MODEL chg = pd base trtpn avisitn avisitn*trtpn /ddfm=kenwardroger htype=3;  
  REPEATED avisitn/subject=usubjid type=&type:;  
  LSMEANS avisitn*trtpn/cl diff;  
  ODS OUTPUT lsmeans=mixedlsmeans1 diffs=diff1;  
run;
```

Step 4: Combine the 100 statistics using Rubin's method to obtain the pooled statistic, which serves as the final statistic for analysis. The reference program for the SAS PROC MIANALYZE procedure is as follows:

```
PROC MIANALYZE DATA=formianalyze;  
  MODELEFFECTS estimate;  
  STDERR stderr;  
RUN;
```

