6.10.1.2. Sensitivity Analysis Methods

The sensitivity analysis of the primary endpoint will be conducted based on the FAS.

Sensitivity Analysis 1: For missing data in the primary endpoint, a Last Observation Carried Forward (LOCF) imputation will be applied, followed by a sensitivity analysis using Analysis of Covariance (ANCOVA). The imputation rules are detailed in Section [6.2.1](#). The model used the change from

baseline in the MDS-UPDRS Part III score at 12 weeks of treatment as the dependent variable, with baseline stable use of levodopa as anti-PD background medication (yes vs. no), baseline MDS-UPDRS Part III score, and treatment group as covariates. Based on the model, calculate the least squares mean of the change from baseline in MDS-UPDRS Part III score at 12 weeks of treatment, along with its 95% CI, the between-group difference in least squares means with its two-sided 95% CI, and the nominal P-value. The reference procedure is as follows:

```
ODS OUTPUT lsmeanc1=lsmeans lsmeandiffcl=lsmeansdiff;
```

```
PROC GLM data=dataset;
```

```
  CLASS trtpn pd;
```

```
  MODEL chg = trtpn pd base/SOLUTION;
```

```
  LSMEANS trtpn/CL STDERR PDIFF COV;
```

```
run;
```

Sensitivity Analysis 2: Assuming the missing data mechanism is missing at random (MAR), a sensitivity analysis will be conducted using the same method as the primary analysis after performing multiple imputation for missing values. For imputation rules, refer to Section [11.1](#) of the SAP Appendix.

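### Appendix A imputes Part III without treatment group, so when Week 12 scores are missing and a dose works, the two multiple-imputation analyses generally give a biased Week 12 difference

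*SAP*

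**What the plan says.** SAP 11.1 imputes in two steps. The Step 1 text lists the predictors: "If applicable, covariates include whether stable levodopa-based anti-PD medication was received at screening (yes vs. no), baseline values (base), and scores at post-baseline visits". It adds that "The order in which these variables enter the procedure step follows the sequence listed above". The variable list in both steps is "VAR pd base week1 week4 week8 week12", and the Step 2 regression statement is "MONOTONE REG(pd base week1 week4 week8 week12". The only BY variable is the imputation number, in Step 2. Treatment appears in none of these places, and no other section adds it.

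The analysis of the completed data does contain treatment. Step 3 fits "MODEL chg = pd base trtpn avisitn avisitn*trtpn". The primary MMRM in SAP 6.10.1.1 likewise has "the treatment group, visit, and the treatment group-by-visit interaction as the fixed effects".

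Two analyses depend on Appendix A. Under Sensitivity Analysis 2 (SAP 6.10.1.2), "a sensitivity analysis will be conducted using the same method as the primary analysis after performing multiple imputation for missing values". Supplementary Analysis 2 (SAP 6.10.1.3) removes data after a concomitant event, treats them as missing, and imputes by the same rules. It is the only analysis of the primary endpoint under the hypothetical strategy.

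**The concern.** The imputation model is narrower than the analysis model, and what it leaves out is the quantity being estimated. A subject who drops out is given later scores from a regression common to all three arms. Any between-arm difference in those scores can come only from differences already seen at earlier visits, shrunk by the regression slopes. The arm-specific change after dropout is lost.

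Sensitivity Analysis 2 is meant to follow the primary method under missing at random (MAR), but the assumption implemented is a different one: later scores do not depend on treatment once the earlier scores are known. For Supplementary Analysis 2, a gap from the primary result would be read as the effect of changing the strategy, when part of it would be imputation error.

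**Working it through.** **Inputs.** From the documents: the predictors and models above; about 50 subjects per arm; and a full analysis set that requires one dose but no post-baseline score (SAP 5). SAP 4 states that the sample size rests on no formal assumptions, so no SD, effect, correlation or dropout is given and there is no plan figure to reproduce. I assume SD 10, baseline-to-Week-12 correlation 0.60-0.85, missingness unrelated to scores and, unless stated, equal across arms.

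**Formula.** Let f be the share missing at Week 12, Δ12 the true difference, and D the average imputed difference among those missing. Then

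expected difference = (1 - f) × Δ12 + f × D.

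Without treatment in the model, and with balanced baselines, D is the sum of pooled slopes times the differences at the visits observed. With treatment in the model, each visit's regression has its own treatment term and D = Δ12.

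**No post-baseline score.** D = 0. A constant effect of -3.5 at f = 0.20 gives 0.8 × (-3.5) = -2.80, a 20% loss. A large-sample run gave -2.83.

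**Hand example.** Equal correlation 0.60, preceding visit as predictor, f = 0.20, one third first missing at each of Weeks 4, 8 and 12. The chained slopes to Week 12 are 0.6³ = 0.216 (last seen Week 1), 0.36 (Week 4) and 0.60 (Week 8). The small between-arm part of the pooled slopes is ignored.

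| Effect at Weeks 1/4/8/12 | D | Expected difference | Against truth |
|---|---|---|---|
| Growing: -0.5/-1.5/-2.5/-3.5 | -(0.108+0.540+1.500)/3 = -0.716 | -2.800 - 0.143 = -2.943 | 15.9% toward zero |
| Constant: -3.5 | -3.5 × 0.392 = -1.372 | -2.800 - 0.274 = -3.074 | 12.2% toward zero |
| Steep wane: -3.5/-3.5/-2.5/-1.0 | -(0.756+1.260+1.500)/3 = -1.172 | -0.800 - 0.234 = -1.034 | 3.4% away from zero |
| Gone: -3.5/-3.5/-2.0/0 | -(0.756+1.260+1.200)/3 = -1.072 | -0.214 | false -0.21 |

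**Range.** The closed form was run over 18 settings (AR(1), compound-symmetry and mixed structures; 200 mg effect equal to or half the 400 mg effect; first missing at Week 4, 8 or 12), for 400 mg against placebo at 20% missing:

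| Effect | All earlier visits as predictors | Preceding visit only |
|---|---|---|
| Growing | 12-17% toward zero | 12-16% toward zero |
| Constant | 1-9% toward zero | 1.5-12% toward zero |
| Steep wane | 14-30% away | 3.5-38% away |
| Gone by Week 12 | false -0.33 to -0.45 | false -0.21 to -0.54 |

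At 10% missing the growing effect is attenuated 6-8% (0.20-0.29 points). A mild wane (-3.5/-3.4/-3.2/-3.0) at 20% is attenuated in 16 of 18 settings. A large-sample run with AR(1) and correlation 0.85 gave -3.00 against -3.0, so the bias can be nil.

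**Trial-size simulation.** 1,000 trials per scenario, 50 per arm, mixed structure, correlation 0.77, 20% missing, 100 imputations. Paired values are all earlier visits / preceding visit only.

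| Truth | Primary MMRM | As written | Treatment added |
|---|---|---|---|
| Growing, -3.5 | -3.48 | -2.97 / -3.02 | -3.48 / -3.48 |
| Constant, -3.5 | -3.54 | -3.33 / -3.34 | -3.53 / -3.53 |
| Steep wane, -1.0 | -1.07 | -1.29 / -1.32 | -1.07 / -1.08 |
| Gone, 0 | -0.02 | -0.41 / -0.44 | -0.02 / -0.01 |
| No effect in any arm | 0.03 | 0.02 / 0.03 | 0.03 / 0.04 |

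Monte Carlo error is about 0.045 per mean.

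**Unequal dropout.** Suppose 30% are missing in each active arm and 10% on placebo, none with a post-baseline score, and true effects are 0 (200 mg) and -5 (400 mg). The pooled observed mean is 0.7 × (-5)/(0.9+0.7+0.7) = -1.52. The ineffective dose then shows (0.3 - 0.1) × (-1.52) = -0.30. Simulation gave -0.37 as written and -0.09 with treatment added, a contrast of -0.28.

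**The case against.** The strongest reply is about reach. One sensitivity and one supplementary analysis are affected, there is no formal test (SAP 6.1), and the shift is well below one standard error. With all earlier visits as predictors, the interval is 0.995-1.008 times the primary's width and coverage is 96-99%. The dropout rate is unknown. Therapies that would trigger the hypothetical strategy are prohibited (protocol 7.2.2), so Supplementary Analysis 2 may have little extra to impute. All of this stands and keeps the point moderate. But the analyses share subjects, so the shift is a systematic gap between reported estimates: for a growing effect at 20% missing it averages 0.42-0.57 points within the same trial, against 0.00 (SD 0.11) once treatment is added.

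The words in the text that make the covariates conditional, and the labelling of the code as a reference program, do not rescue the plan, because text and code both omit treatment.

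Three stronger inferences are not supported:

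- That the primary result is biased. It uses no imputation.
- That the imputation always understates the effect. Direction depends on the time course and on dropout by arm.
- That Sensitivity Analysis 2 fails the protocol's call for different imputation mechanisms (11.4.3). That phrase can mean methods, and the SAP supplies two, LOCF and multiple imputation.

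**Conclusion.** The concern holds for Sensitivity Analysis 2 and Supplementary Analysis 2 only, and only when Week 12 data are missing and at least one dose has an effect. The bias is toward zero for a growing or constant effect. It is away from zero, or a false benefit, when an early effect fades, and near zero for some mild wanes. An ineffective dose can show a small spurious difference if dropout is unequal. With no effect in any arm there is no bias.

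The sizes are illustrations, not bounds: the 18 settings exclude subjects with no post-baseline score, who would push a constant effect to about a 20% loss at 20% missing. They also assume dropout unrelated to scores, which may not describe the data deleted under Supplementary Analysis 2. This should be fixed, but the trial's main estimate does not rest on it.

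**What to change.** Before unblinding, amend SAP Appendix A:

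- Name randomised treatment group in the covariate sentence.
- Step 1: add two 0/1 indicators (200 mg, 400 mg) ahead of `week1` in the variable list, with four placeholders before the four visit entries in ROUND, MIN and MAX.
- Step 2: put `trtpn` in CLASS and in VAR ahead of `week1`, with three placeholders, and list only the four visit scores in MONOTONE REG. Order matters: treatment placed after Week 12 would inform no visit.
- Reconcile the sentence "The missing values at post-baseline visits will be imputed using the results from the immediately preceding visit" with the variable list, which supplies baseline and all earlier visits. This mismatch does not cause the bias. Using all earlier visits matches the information in the primary MMRM; the preceding-visit reading makes the interval 0-17% wider than the primary's even with treatment added.
- Test-run the code on dummy treatment codes.

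The cost is one or two sentences and a few code terms, with no protocol amendment and no new data. The corrected Sensitivity Analysis 2 will add little beyond the primary MMRM. The gain is that both imputation analyses follow the same MAR model as the primary, so a gap between Supplementary Analysis 2 and the primary no longer contains this error. Their validity still rests on MAR.
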